**HDCLARITY SCHEDULE OF EVENTS**

Visit Type	Year 0 			Years 1, 2, 3 	
	Annual Screening	Annual Sampling	Optional Repeat Sampling	Annual Screening	Annual Sampling
Visit Window	-30 to -1 days	Day 0	Day 28 - 56	Annually $\pm$ 2 months	Within 30 days of Annual Screening Visit
Study Procedure					
Informed Consent / Assent	X				
Confirm Continued Consent / Assent		X	X	X	X
Inclusion/Exclusion Criteria review	X	X	X	X	X
Demographics update	X			X	
Confirm Enroll-HD core assessments completed within last three months	X			X	
Brief Physical Exam	X	X	X	X	X
Medical History update	X	X	X	X	X
Prior/Concomitant Medication update	X	X	X	X	X
Full Neurological Examination	X			X	
Focused Neurological Examination		X	X		X
Total Motor Score (TMS)		X	X		X
Vital Signs (BP, pulse, body temp)		X	X		X
Safety Laboratory Assessments	X			X	
Urine Pregnancy Test 	X	X	X	X	X
Adverse Events (AE)		X	X		X
Final Eligibility Check		X	X		X
Lumbar CSF Collection		X	X		X
Venous Blood Draw 		X	X		X
CSF and Blood Sample Processing		X	X		X
CSF QC Processing		X	X		X
Telephone Follow-Up within 1-3 days (concomitant medication and AEs)		X	X		X

 This sequence of visits will continue such that Informed Consent/Assent will be sought again every fourth year

 Urine pregnancy test to be performed for females of child bearing potential unless the participant is post-menopausal or not sexually active

 Obtain venous blood sample immediately after CSF collection is complete

### 8.1.1 Annual Screening Visit

- The study will be described in detail to prospective participants and informed consent or assent will be obtained at the first Annual Screening Visit. Continued consent will be confirmed at all subsequent Annual Screening Visits.
- Medical history update since the last Enroll-HD study visit, including medication history and co-morbidities, is obtained.
- Demographic information update since the last Enroll-HD study visit.
- Weight measurement (only if weight appears to vary significantly (>3kg/6.5lb) since last Enroll-HD visit).
- Perform a full neurological examination as described in the HDClarity Laboratory Manual, as well as a brief general physical examination. Evidence of possible bleeding tendency such as bruises or petechial rash should be noted.
- Urine pregnancy test for females of child bearing potential (excludes females who are post-menopausal or not sexually active).
- Up to 15 ml of venous blood is drawn according to local clinical standards and procedures, and routine blood tests performed by a local accredited clinical laboratory:
  - Full blood count
  - Clotting profiles: PT and APTT
  - CRP

If the blood count or clotting profiles are more than 10% outside the lab's normal range for the following: white cell count, neutrophil count, lymphocyte count, hemoglobin (Hb), platelets, prothrombin time (PT) and activated partial thromboplastin time (APTT), or if CRP is greater than 2× the upper limits of normal the participant will not be booked for an Annual Sampling Visit. The Site Principal Investigator will act on any abnormalities according to clinical judgment.

If participants do not fulfill all inclusion criteria, they may be rescheduled to repeat some or all of the screening assessments above with the prior approval of the Chief Investigator.

If these assessments confirm all the eligibility requirements are met for the study, a date will be given via a telephone call for the Annual Sampling Visit.

### 8.1.2 Annual Sampling Visit

- Participants will be required to fast and drink only water for at least six hours, or overnight, before the scheduled time of the Annual Sampling Visit. Compliance with instructions to fast is recorded.
- If participant has not complied with pre-sampling instructions such as fasting or medications, or if the Site Principal Investigator deems the sampling procedure unsafe, unwise or unlikely to produce satisfactory samples, the participant may be sent home, and the sampling rescheduled at the discretion of the Site Principal Investigator.
- Participant continued consent or assent to participate and eligibility are confirmed and recorded.
- The results of the routine laboratory examination are reviewed and recorded.

- Medical and concomitant medication history is updated.
- Urine pregnancy test for females of child bearing potential (excludes females who are post-menopausal or not sexually active).
- Measurement of vital signs.
- Weight measurement (only if weight appears to vary significantly (>3kg/6.5lb) since last Enroll-HD visit).
- Any changes to medical history and medication are noted.
- A focused neurological examination is performed as described in the HDClarity Laboratory Manual and the brief physical exam is repeated for safety.
- The Total Motor Score (TMS) of the UHDRS is performed.
- Lumbar CSF Collection is performed. (See Section 9.1 for instructions)
- Venous blood sampling is performed immediately after CSF collection is complete. (See Section 9.2 for instructions)
- AE recording
- Process CSF, Serum and Plasma samples per Sections 10.1, 10.2 and 10.3, respectively.
- Perform sample quality control (QC) per Section 12.
- Store samples per Section 11.

#### **8.1.2.1 Participant Discharge**

Participants are observed for potential complications as per routine clinical practice and discharged once appropriate. Record any AEs.

Participant is discharged by nurses with instructions for over the counter pain medication and hydration in the event of headache.

#### **8.1.3 Follow-up Telephone Call**

Participants are contacted within 24 to 72 hours following an Annual Sampling Visit to collect any AE and/or concomitant medication data. If an AE is reported and is possibly or probably related to study procedures it must be followed until the event resolves, the condition stabilizes, the event is otherwise explained, or the participant is lost to follow up.

#### **8.1.4 Optional Repeat Sampling Visit**

- This visit is optional. Participant continued consent or assent to participate and eligibility are confirmed and recorded.
- This visit should be scheduled 4 - 8 weeks following the Annual Sampling Visit during the first year of enrollment.
- Participants will be required to fast and drink only water, for at least six hours, or overnight, before the scheduled time of the Optional Repeat Sampling Visit. Compliance with instructions to fast is recorded. If the participant did not fast, they will be sent home, and the procedure rescheduled.

- The results of the routine laboratory examination are reviewed and recorded.
- Urine pregnancy test for females of child bearing potential (excludes females who are post-menopausal or not sexually active).
- Measurement of vital signs.
- Weight measurement (only if weight appears to vary significantly (>3kg/6.5lb) since last Enroll-HD visit).
- Any changes to medical history and medication are noted.
- A focused neurological examination is performed as described in the HDClarity Lab Manual and the brief physical exam is repeated for safety.
- The TMS of the UHDRS is repeated.
- Lumbar CSF Collection is performed. (See Section 9.1 for instructions)
- Venous blood sampling is performed immediately after CSF collection is complete. (See Section 9.2 for instructions)
- AE recording.
- Process CSF, Serum and Plasma samples per Sections 10.1, 10.2 and 10.3, respectively.
- Perform sample QC per Section 12.
- Store samples per Section 11.

#### **8.1.4.1 Participant Discharge**

Participants are observed for potential complications as per routine clinical practice and discharged once appropriate. Record any AEs.

Participant is discharged by nurses with instructions for over the counter pain medication and hydration in the event of headache.

#### **8.1.5 Follow-up Telephone Call 2**

Contact participant 24 to 72 hours following Optional Repeat Sampling Visit to collect any AE and/or concomitant medication data. If an AE is reported and is possibly or probably related to study procedures it must be followed until the event resolves, the condition stabilizes, the event is otherwise explained, or the participant is lost to follow up.

### **9. Sample Collection Procedures**

#### **9.1 Lumbar CSF Collection**

Up to 20 ml of CSF for participants  $\geq 18$  years of age and 5-10 ml for participants  $< 18$  years of age will be collected by a lumbar puncture procedure as described in the HDClarity Laboratory Manual, recording the collection time.

## **9.2 Venous Blood Collection**

Venous blood is drawn immediately after CSF collection is complete, recording the time. Up to 50 ml of blood from participants  $\geq 18$  years of age and 30 ml for participants  $< 18$  years of age will be collected as described in the HDClarity Laboratory Manual.

If venepuncture with vacuum tubes proves challenging, a needle and syringe may be used and the blood transferred immediately into the vacuum tubes, observing safety precautions.

## **10. Sample Processing Procedures**

### **10.1 CSF Sample Processing**

CSF samples must be processed according to the procedures specified in the HDClarity Laboratory Manual.

### **10.2 Serum Sample Processing**

Serum samples must be processed according to the procedures specified in the HDClarity Laboratory Manual.

### **10.3 Plasma Sample Processing**

Plasma samples must be processed according to the procedures specified in the HDClarity Laboratory Manual.

## **11. Sample storage and shipment**

Storage and shipment of the samples must be handled according to the procedures specified in the HDClarity Laboratory Manual.

## **12. Sample Quality Control**

Quality control will be performed on all samples according to the procedures specified in the HDClarity Laboratory Manual and/or at a central laboratory.

## **13. Medical Monitoring**

The Medical Monitor should be contacted directly to report medical concerns or questions regarding safety. The medical monitor can be contacted via email at [[contact]](mailto:[contact]).

## **14. Adverse Event Reporting and Documentation**

### **14.1 Adverse Events**

An adverse event (AE) is any untoward medical occurrence during a clinical investigation and that does not necessarily have a causal relationship with study treatments or procedures. An AE is therefore any unfavorable and unintended sign (including an abnormal laboratory finding), symptom or disease temporally associated with the administration of study procedures.

The Site Principal Investigator will probe, via discussion with the participant, for the occurrence of AEs during each participant visit, after the Annual Screening Visit, and record the information in the site's source documents. AEs will be recorded in the

participant eCRF. AEs will be described by duration (start and stop dates and times), severity, outcome, treatment and relation to study procedures if applicable, or if unrelated, the cause.

### 14.1.1 AE Severity Grading

The severity of an AE will be graded on a 5-point scale (Common Terminology Criteria for Adverse Events v3.0 (CTCAE; [http://ctep.cancer.gov/protocolDevelopment/electronic\\_applications/ctc.htm](http://ctep.cancer.gov/protocolDevelopment/electronic_applications/ctc.htm)) defined as follows:

Grade 1	Mild AE
Grade 2	Moderate AE
Grade 3	Severe AE
Grade 4	Life-threatening or disabling AE
Grade 5	Death related to AE

### 14.1.2 AE Relationship to study procedures

The relationship of an AE to the study procedures will be evaluated according to the following guidelines:

**Probable:** This category applies to AEs which are considered with a high degree of certainty to be related to the study procedure. An AE may be considered probably related to the study procedure if:

1. It follows a reasonable temporal sequence from administration of the study procedure;
2. It cannot be reasonably explained by the known characteristics of the participant's clinical state, or by environmental or toxic factors;
3. It follows a known pattern of response to the study procedure;

**Possible:** This category applies to those AEs in which the connection with the study procedure appears unlikely but cannot be ruled out with certainty. An AE may be considered as possibly related if it has at least two of the following:

1. It follows a reasonable temporal sequence from the study procedure
2. It may readily have been produced by the participant's clinical state, or by environmental or toxic factors;
3. It follows a known response pattern to the study procedure.

**Unrelated:** This category applies to those AEs which are judged to be clearly and incontrovertibly due to extraneous causes (disease, environment, etc.) and do not meet the criteria for study procedure relationship listed under possible or probable.

## 14.2 Serious Adverse Events

A Serious Adverse Event (SAE) is defined as any AE that results in any of the following outcomes:

- death
- a life-threatening adverse experience
- inpatient hospitalization or prolongation of existing hospitalization
- a persistent or significant disability/incapacity

- a congenital anomaly/birth defect
- any other serious medical occurrence

Other important medical events may also be considered an SAE when, based on appropriate medical judgment, they jeopardize the participant or require intervention to prevent one of the outcomes listed.

An AE is considered to be life-threatening if, in the view of the Site Principal Investigator, the participant was at immediate risk of death from the reaction as it occurred. It does not include a reaction that, had it occurred in a more serious form, might have caused death.

Serious Adverse Events will be documented from the point of enrollment until the participant is exited from the study. If a participant enrolls multiple times, AEs and SAEs will be documented from the point of each new consent until the final study visit for that enrollment.

Information recorded and reported shall include:

- A description of the event
- the date of event onset
- The relatedness of the event to the procedure
- The expectedness of the event
- The outcome of the event
- The date the event was first noticed by, or reported to the Site Principal Investigator

All ongoing Serious Adverse Events will be followed-up until the last study visit and post study follow-up is described in Section 14.4 below.

### **14.2.1 Serious Adverse Event Reporting**

SAEs (as defined in Section 15.2) must be reported to the designated Medical Monitor immediately, and also to the Sponsor by email, and in no case later than within 24-hours of awareness of the event.

All SAEs that occur (whether or not related to study procedures) will be documented. The collection period for all SAEs will begin from the Annual Sampling Visit and end after procedures for the final study visit have been completed.

In accordance with the standard operating procedures and policies of the local IRB/ERB, the Site Principal Investigator will report SAEs to the IRB/ERB.

### **14.3 Reporting incidents**

An incident in a research study is:

- Something that should not have happened OR
- Something that should have happened but didn't which, in either case, significantly affects any of the following:
  - the rights and wellbeing of the study participant,
  - the scientific value of the study,

- the compliance of the study with all applicable legal rules or ethics guidance including, as applicable, the Data Protection Act, the General Data Protection Regulation, and the Human Tissue Act, or
- the reputation of the Sponsor.

This includes a requirement to report all serious breaches of protocol or GCP (if applicable).

All incidents must be reported through the appropriate host site incidents reporting system. For any host site where no United Kingdom National Health Service Trust is involved, the incident should be reported by completing the “Incident Report Form” that may be found at <http://www.ucl.ac.uk/jro/postapproval>.

#### **14.4 Post-study Follow-up of Adverse Events**

All AEs, including clinically significant physical examination findings and SAEs, must be recorded in the Electronic Data Capture system (EDC) and any AE that is possibly or probably related to study procedures must be followed until the event resolves, the condition stabilizes, the event is otherwise explained, or the participant is lost to follow up. If resolved, a resolution date should be documented on the eCRF and in the source documents. The Site Principal Investigator is responsible for ensuring that follow up includes any supplemental investigations as may be indicated to elucidate the nature and/or causality of the AE. This may include additional laboratory tests or investigations, histopathological examinations, or consultation with other health care professionals as is medically indicated.

### **15. Statistical Methodology**

#### **15.1 Determination of Sample Size**

The CSF and plasma samples collected in this study will be the basis for future biomarker analysis studies. Each of those studies will require a specific power calculation to determine how many samples to include in the analysis. However, the open-ended nature of biomarker discovery and validation and the purpose of HDClarity as a biorepository favours placing no upper limit on the number of participants that may be enrolled.

While most of the biomarker development focus is on earlier stages of the disease, it may also be important to assess some biomarkers at more advanced stages. Only sites with access to in-patient facilities will likely be able to recruit this cohort.

For some biomarkers, it may be important to understand the stability of the biomarker within participants over relatively short time periods. Thus, up to approximately 20% participants will be invited to return for an Optional Repeat Sampling Visit 4-8 weeks after their Annual Sampling Visit during their first year of enrollment. Other biomarker discovery and analysis, e.g. analysis of disease progression, may require comparison of samples at longer intervals and these will be available from the longitudinal sampling visits.

## **16. Study Management**

### **16.1 Roles and responsibilities**

Except where dictated by convention, statute or GCP, the roles and responsibilities of all parties involved in the study will be set forth in study site agreements or other contracts or subcontracts agreed by the parties concerned.

### **16.2 Ethics and Regulatory Considerations**

This study will be conducted according to Good Clinical Practice (GCP), 21 CFR Part 50, (Protection of Human Subjects), 21 CFR Part 56 (Institutional Review Boards), International Conference on Harmonisation Guidance for Industry (ICH guidelines), E6 Good Clinical Practice: Consolidated Guidance, the Nuremberg Code, and the Declaration of Helsinki.

Sites will be responsible for obtaining all appropriate approvals from IRBs/ERBs, supported by a CHDI-approved informed consent form. ERB and/or IRB approval will be sought for each site in each country as per their regulations prior to the start of study activities at that site.

#### **16.2.1 Audits and Inspections**

CHDI, regulatory authority, Sponsor or IRB/ERB may visit the study site at any time during the study or after completion of the study to perform audits or inspections. The purpose of such an audit or regulatory inspection is to systematically and independently examine all study-related activities and documents to determine whether these activities were conducted according to the protocol, GCP, ICH guidelines, and any other applicable regulatory requirements. Site Principal Investigators should contact the Chief Investigator and CHDI immediately if contacted by a regulatory agency about an inspection at their site.

#### **16.2.2 Ethics Committee Approval**

This protocol and any amendments will be submitted to a properly constituted IRB/ERB, in accordance with the ICH guidelines, the applicable European Directives and local legal requirements, for approval of the study. Approval must be obtained in writing before the first participant can be recruited.

### **16.3 Insurance**

University College London, the Sponsor, holds insurance against claims from participants for harm caused by their participation in this study. Participants may be able to claim compensation if they can prove that the Sponsor has been negligent. However, if this study is being carried out in a hospital, the hospital continues to have a duty of care to the participant of the study. The Sponsor does not accept liability for any breach in the hospital's duty of care, or any negligence on the part of hospital employees. This applies whether the hospital is an NHS Trust or otherwise.

### **16.4 Informed Consent Procedure**

All participants must give informed consent prior to undertaking study procedures and these informed consents must be obtained by clinical site staff using approved processes according to all applicable laws and regulations on GCP. At a minimum, the consent process will involve:

1. Provision of written, ERB and/or IRB-approved information about the study to potential participants;
2. Potential participants permitted sufficient opportunity to read the information and consider the options without maximum but with a recommended minimum of 24 hours;
3. Potential participants permitted sufficient opportunity to ask questions and receive satisfactory answers from the site study team;
4. Potential participants' comprehension verified before signing a consent form; and
5. The voluntary signing of a consent form and countersigning by the study site personnel undertaking the consent process.

In the event that a site wishes to enroll participants with impaired capacity, specific ERB and/or IRB approval will be sought in advance before such participants are enrolled and a Legally Authorised Representative will sign on behalf of the participant.

In the case of underage participants, consent will be obtained from the parent or guardian, together with informed assent from the underage participant in compliance with local regulations and requirements.

Informed consent obtained at the beginning of the study will be valid for three years. The participants will be re-consented for the study after that every fourth year should they wish to continue participation. The participant is encouraged to provide a CSF sample every year but are at no obligation to do so. If a participant does not attend an Annual Screening and Sampling Visit for consecutive three years, they will be discontinued from the study. They can re-enroll in the study if they wish to do so.

Signed consent forms will be maintained in a secure designated location at the site.

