### **Informed consent procedure**

All participants must give informed consent, or assent if underage, prior to undertaking study procedures and these informed consents and assents must be obtained by clinical site staff using approved processes. Signed consent and assent forms will be maintained in a secure designated location at the site.

Participants will consent or assent for 3 years initially, equivalent to 4 Annual Screening and 4 Annual Sampling Visits (i.e. year 0, 1, 2 and 3). They may renew their informed consent or assent in the fourth year in order to continue participating in the study.

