## **8. Study Procedures**

Participants will attend two annual study visits, an Annual Screening Visit followed by an Annual Sampling Visit. They may also attend an optional visit during their first year of enrollment, an Optional Repeat Sampling Visit. Participants will attend annual visits at regular intervals after the first Annual Screening Visit (i.e. at 1, 2, 3 years and so on)  $\pm$  2 months. The study procedures for each visit type are described in the Schedule of Events table below.

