### **8.1 Description of Study Assessments**

The Annual Screening and Annual Sampling Visits should be no more than 30 days apart. The Annual Screening Visit may occur on the same day as an Enroll-HD visit. The Optional Repeat Sampling Visit will occur within 4-8 weeks of the Annual Sampling Visit during the first year of enrollment. Participants will be encouraged to complete all annual visits; however, they are under no obligation to take part and will be able to skip annual visits without being discontinued from the study for up to three years.

Information regarding occurrence of adverse events (AEs) and Serious Adverse Events (SAEs) will be captured each year in the period from the Annual Screening Visit until the follow-up phone call after the associated Annual Sampling Visit (or Optional Repeat Sampling visit, if applicable). Duration (start and stop dates and times), severity/grade, outcome, treatment and relation to study procedures will be recorded on the electronic case report form (eCRF).

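### Does the three-year consent term in Section 16.4 run out before the Year 3 lumbar puncture it is meant to cover?

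*Protocol*

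**What the plan says.** Section 16.4 gives the initial term as a length of time: "Informed consent obtained at the beginning of the study will be valid for three years". It continues: "The participants will be re-consented for the study after that every fourth year should they wish to continue participation".

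Section 4.2.1, under its informed consent heading, gives the same term and ties it to visits: "Participants will consent or assent for 3 years initially, equivalent to 4 Annual Screening and 4 Annual Sampling Visits", which it lists as years 0, 1, 2 and 3. Renewal follows: "They may renew their informed consent or assent in the fourth year in order to continue participating in the study".

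Two places fix the clock. Section 8.1.1 says that "informed consent or assent will be obtained at the first Annual Screening Visit. Continued consent will be confirmed at all subsequent Annual Screening Visits". Section 8 says: "Participants will attend annual visits at regular intervals after the first Annual Screening Visit (i.e. at 1, 2, 3 years and so on"), with a margin of two months either way. Section 8.1 adds: "The Annual Screening and Annual Sampling Visits should be no more than 30 days apart". For Years 1 to 3 the Schedule of Events gives the sampling window as "Within 30 days of Annual Screening Visit".

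In the Schedule, obtaining consent is marked only in the Year 0 Annual Screening column. All other visits carry confirmation of continued consent. Footnote 1 says that the sequence repeats, with consent sought anew every fourth year. Section 8.1.2 has continued consent and eligibility confirmed and recorded at each Annual Sampling Visit.

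**The concern.** The consent term and the visit calendar start on the same day. If Section 16.4 is read alone and literally, the term expires on the exact target date of the Year 3 Annual Screening Visit. Any Year 3 screening in the later half of its window, and any sampling that follows an on-time screening, would then fall outside the term. The equivalence in Section 4.2.1 between three years and four pairs of visits would also fail under the protocol's own windows.

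What would be at stake is a lumbar puncture done after written consent had expired. Section 16.4 requires consent before study procedures, and the cohorts include minors and participants consented by a representative. A monitor who applied the bare three-year term could record an in-window Year 3 puncture as a consent deviation. The references to a fourth year add to the doubt. Counted from consent, the fourth year runs from month 36 to month 48, so it already contains an on-time or late Year 3 visit.

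**Working it through.** **Inputs**
- Consent term: 3 years = 36 months (Section 16.4).
- Start of the term and of the visit calendar: first Annual Screening Visit (Sections 8.1.1 and 8).
- Year 3 screening window: 36 ± 2 months (Section 8; Schedule of Events).
- Sampling: up to 30 days after screening (Section 8.1; Schedule of Events).
- Average month: 365.25 / 12 = 30.4375 days.

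**The protocol's own equivalence.** On target dates, visits at years 0, 1, 2 and 3 make four pairs spanning three years. The count of four is right. The windows are what push visits beyond month 36.

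**Latest in-window Year 3 visits**
- Screening: 36 + 2 = month 38, which is 2 × 30.4375 = 60.9 days past the term. Calendar dates give 59 to 62 days, over every consent date from 1 November 2021 to 31 October 2026.
- Sampling, if it may follow a late screening by 30 days: 60.9 + 30 = 90.9 days past the term (59 + 30 = 89 to 62 + 30 = 92 on calendar dates).
- Sampling, if the two-month margin limits both annual visits: at most 60.9 days past the term.
- Screening exactly at month 36, sampling 1 to 30 days later: 1 to 30 days past the term.

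The 61 and 91 days are two maxima under two readings of the window. They are not a range of expected lateness.

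**Example.** Consent on 10 January 2022 reaches three years on 10 January 2025. The latest Year 3 screening is 10 March 2025 (59 days later) and the latest sampling is 9 April 2025 (89 days later).

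**How often it can happen.** The earliest in-window Year 3 screening is month 34, so sampling can also fall inside the term. The full 30-day allowance ends by month 36 only if screening takes place at least 30 days before the target date. That is (61 − 30) / 122 = 31 / 122, or about 25% of the screening window. An overrun is therefore ordinary under the literal reading, though not certain.

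**Passages side by side**

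| Place | What it implies for Year 3 |
|---|---|
| Section 16.4 | Term ends at month 36 if read alone |
| Section 4.2.1 | Year 3 screening and sampling are inside the initial consent |
| Schedule, Years 1 to 3 | Consent is confirmed, not obtained anew |
| Schedule, footnote 1 | The Year 0 to 3 sequence repeats, so the next signed consent opens the next cycle, at Year 4 screening |
| Section 8.1.2 | Continued consent is confirmed and recorded on the sampling day |

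All but the first row point to a visit-based term or fit with one. Only Section 16.4, taken without Section 4.2.1, points the other way.

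**The case for a change.** The case for rewording is that intent expressed in one section does not alter a plain term in another, and Section 16.4 is the section devoted to consent. Confirming continued consent is listed separately from obtaining it, and nothing says that confirmation extends an expired term. No sentence names Year 4 as the re-consent visit, so one site might re-consent at Year 3 and another at Year 4. The correction would be a few words, with no added visit or consent step.

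Part of this stands. The calendar sums are right, Section 16.4 omits the equivalence that Section 4.2.1 supplies, and the label Year 4 does not appear.

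The rest is weaker. The protocol nowhere states a hard cut-off at month 36 that overrides its own visit-based definition. The re-consent visit can be read off the Schedule, because the only column with a consent mark is the screening visit that opens the cycle. The strict reading does not leave a puncture without consent either: time past month 36 is then the fourth year, when Section 4.2.1 offers renewal and Section 16.4 calls for re-consent. A site that re-consents early, at Year 3, does no harm. Whether any participant's consent would lapse depends on the signed form, which these documents do not include.

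**Conclusion.** No change to the plan follows. This is a clerical inconsistency: Section 16.4 shortens a rule that Section 4.2.1 and the Schedule of Events give in full. On the literal reading, the in-window Year 3 Sampling Visit can pass the three-year mark by at most about 61 or about 91 days, depending on whether the two-month margin limits sampling. On the reading that the rest of the protocol supports, the initial consent covers Years 0 to 3 and the overrun is nil.

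Rewording would change nothing that the study does or concludes. Visits, consent steps, cohorts, sample numbers, data and error rates would stay as they are, and a participant's willingness is already checked and recorded on the day of the puncture.

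The conclusion assumes that sites read Section 16.4 together with Section 4.2.1 and the Schedule, and that the consent form sets no stricter expiry date of its own.
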